11.3 Sample Size Considerations

We expect to enroll 15 patients for Intervention 1 and 15 patients for Control for Phase I, and 15 patients for Intervention 2 and 15 patients for Control for Phase II. For the primary endpoint of Q13 and Q16 in each of the two phases, the numeric difference of post- vs. pre- responses will be compared between Intervention and Control arms. This sample size will achieve 82.8% power to detect an effect size of 1.1 at 5% significance level using a two-sided two-sample equal-variance t-test.

11.3.1 Accrual Estimates

30 patients will be accrued into each phase of the trial, resulting in 60 total patients enrolled.

11.4 Evaluation of Safety

Safety will be assessed on a per participant basis as each patient will only be tracked for one visit. There is no statistical analysis of safety planned.

12 Source Documents and Access to Source Data/Documents

Study staff will maintain appropriate medical and research records for this study, in compliance with ICH E6, and regulatory and institutional requirements for the protection of confidentiality of participant information. Study staff will permit authorized representatives of SKCC and regulatory agencies to examine (and when required by applicable law), to copy research records for the purposes of quality assurance reviews, audits, and evaluation of the study safety, progress and data validity.

Source data will be maintained via the electronic medical record (EMR) and the Qualtrics survey platform. The EMR will maintain recorded vital signs and Qualtrics will maintain all survey data, including demographics. Qualtrics is a HIPAA compliant platform. Survey responses will be accessible to the PI and one Co-I for review and analysis.

Physical copies of the randomization envelopes, provided by the Biostatistics department, will also be retained for reference.

13 Quality Control and Quality Assurance

The PI, in conjunction with the research coordinator, [name], will provide training for all study staff on appropriate language for communicating with patients, proper implementation of interventions, and usage of Qualtrics survey software. This will include an introduction to the VR hardware and guided meditation software. All study staff will follow the same plan for onboarding patients to interventions to assure consistency in care.

Source materials will be evaluated weekly, or as problems arise, to ensure data entry is maintained and information remains organized. The research coordinator will be responsible for addressing Qualtrics quality assurance issues. All other compliance will be assessed by the PI.

14 Ethics/Protection of Human Participants

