| Précis: | Patients undergoing a bone marrow biopsy aspiration (BMBA) will trial possible interventions to decrease their distress and pain , as suggested by a previous patient survey conducted with this population. The study will assess both pre-intervention and post-intervention distress scores and a post-intervention pain score. Patient satisfaction will also be assessed to determine overall patient experience. Each intervention will be compared to a control group to validate if one or both interventions are valuable to offer to patients in the future. |
| Objectives: | 
Primary: Trial VR and environmental interventions to determine if either result in a reduction in patient distress during BMBA.
 
Secondary: Determine if either intervention results in decreased pain or improved satisfaction scores.
 |
| Population: | 
Young adult to geriatric patients with hematologic malignancies of varying health statuses and demographic groups
 
Most patients have hematological cancers, including leukemia, lymphoma, and multiple myeloma.
 |
| Phase: | N/A |
| Number of Sites: | TJU |
| Description of Intervention: | 
Two interventions will be trialed. The first intervention is virtual reality (VR) guided mediation. Patients will be provided with wireless VR headsets that contain a guided meditation application. The application allows users to select their preferred music, visual setting, and a topic for meditation.
 
The second intervention is environmental changes. A nature themed wall mural decal will be installed in the BMBA room and the in-room computer will play music from Pandora. A selection of suggested stations will be provided, with the option for outside selections.
 |
| Study Duration: | 10 months |

| | |
|---|--|
| Participant Participation Duration: | Approximately 45 minutes, the duration of a normal BMBA visit, including procedure |
| Estimated Time to Complete Enrollment: | 6 months |

Schematic of Study Design:

1 Introduction

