Our hypothesis is that patients undergoing bone marrow biopsy and aspiration (BMBA) who receive distraction techniques (room décor, music, and virtual reality) will have lower levels of distress and pain than patients who receive only the standard of practice care. Additionally, these patients will have higher levels of satisfaction with their overall experience. This study aims to evaluate pre-procedure and post-procedure distress and

pain scores, and post-procedure satisfaction ratings to determine if one or both of the selected interventions are valuable to employ in-clinic for the entire patient population.

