1.3 Potential Risks and Benefits

1.3.1 Potential Risks

Potential risks vary based on intervention arm.

Intervention 1: Virtual reality may cause symptoms associated with motion sickness, including nausea, dizziness, disorientation, and vertigo.²⁹ Mild eyestrain or headaches may also occur.

Intervention 2: There are no known risks associated with music therapy or décor changes.

Participants in all study arms will undergo a BMBA procedure as part of their standard care. Potential risks of bone marrow biopsies are bruising and pain at the biopsy site, discomfort at the site during or post-procedure, prolonged bleeding, and infection.

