3.2 Number of Participants

60 total patients will be enrolled in the study. For Phase I, 15 patients will enroll in Intervention 1 and 15 patients will enroll in the control arm. For Phase II, 15 patients will enroll in Intervention 2 and 15 patients will enroll in the control arm.

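### No by-arm summary of adverse events is planned, so the randomised control is not used to put the VR symptoms named in section 1.3.1 in context

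*Combined protocol and SAP*

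**What the plan says.** Section 11.4 consists of two sentences: "Safety will be assessed on a per participant basis as each patient will only be tracked for one visit", and then "There is no statistical analysis of safety planned".

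Section 1.3.1 gives the headset its own risks: "Virtual reality may cause symptoms associated with motion sickness, including nausea, dizziness, disorientation, and vertigo", and "Mild eyestrain or headaches may also occur". It names no known risks for the music and décor intervention. No expected rates are given for any of these symptoms.

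The Précis in the synopsis states the purpose: "Each intervention will be compared to a control group to validate if one or both interventions are valuable to offer to patients in the future". Section 1.2 ties the same judgement to distress and pain scores and to "post-procedure satisfaction ratings to determine if one or both of the selected interventions are valuable to employ in-clinic". Section 11.2 lists the between-arm comparisons: distress (Q13, Q16), pain (Q12, Q17) and satisfaction (Q18). No harm variable is among them. Section 15.3 announces a report after each phase and a final report, without stating any safety content.

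Section 3.2 gives the arm sizes: "For Phase I, 15 patients will enroll in Intervention 1 and 15 patients will enroll in the control arm". Phase II has the same sizes.

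**The concern.** Several of the symptoms attributed to the headset are hard to tell from effects of the biopsy. Section 8.1.2 puts both kinds in one list of potential adverse events: lightheadedness around the procedure is there, and so is dizziness. Section 8.3.1 asks for a judgement of relatedness on each event, but one of its criteria, recurrence on re-challenge, is of little use in a single visit of about 45 minutes. The concurrent randomised control is the best available means of separating headset effects from biopsy effects, and the plan does not use it for that.

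At stake is the completeness of the evidence behind a recommendation. Benefit would be reported as a comparison with control and harm as a set of individual cases. With arms this small, a reader given no interval could also take an absence of events for evidence that the symptoms are rare.

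**Working it through.** **The plan's own figure.** Section 11.3 gives 82.8% power for 15 v 15, effect size 1.1, two-sided 5% t-test. The noncentral t calculation gives 82.84%, so the figure reproduces. It concerns distress only. The plan states no safety figure.

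**Does any other section supply a comparison by arm?**
- 8.2 sets the follow-up window: 7 days for non-serious events and 30 days for serious ones. It has no summary.
- 8.3 covers relatedness, expectedness, CTCAE grade and treatment of each event. All are recorded per event.
- 8.4.1 and 8.4.2 send Grade 1 and 2 events to continuing review by the IRB and quarterly review by the DSMC. No by-arm layout is specified.
- 8.5 counts patients with Grade 4 and 5 events or with SAEs, with no split by arm. Mild nausea or headache would not enter it.
- Appendix B, Q19 to Q23, is shown to intervention patients only. No survey item asks about symptoms. Q24 is free text.
- 11.2 and 15.3 contain no safety variable.

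None of these is comparative.

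**What 15 patients per arm can show.** Inputs: n = 15 per arm (3.2). Event rates are assumptions, because the documents give none. All 15 patients are taken to contribute data.

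1. Upper limit after zero events (Clopper-Pearson, two-sided 95%): 1 − 0.025^(1/15) = 0.218, or 21.8%.
2. Other exact 95% intervals: 1/15 gives 0.2% to 31.9%, 2/15 gives 1.7% to 40.5%, and 3/15 gives 4.3% to 48.1%.
3. Chance of seeing no event when the true rate is p, (1 − p)^15: p = 5%, 46.3%; p = 10%, 20.6%; p = 20%, 3.5%.
4. Fisher's exact test, two-sided, x/15 v 0/15, p = 2 × C(15,x)/C(30,x):
   - x = 4: 2 × 1365/27405 = 0.0996
   - x = 5: 2 × 3003/142506 = 0.042

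   So 5 v 0 is the smallest excess over zero that reaches p < 0.05.
5. Power of that test by full enumeration, at assumed VR and control rates:
   - 20% v 0%: 16%
   - 30% v 0%: 49%
   - 20% v 5%: 8%
   - 30% v 5%: 28%
   - 50% v 5%: 74%
6. A risk difference as the table would show it: 3/15 v 0/15 is 20 percentage points, Newcombe 95% interval −4 to 45.

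Steps 4 and 5 explain why a test adds little. Steps 1 to 3 and 6 show what a descriptive table with intervals would tell the reader.

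**The case against.** The strongest defence is that safety is in fact evaluated. Section 11.4 keeps assessment of each participant. Section 8 keeps relatedness, CTCAE grading, DSMC and IRB review and a halting rule, and section 4.5 allows termination for unacceptable risk. A reader might infer from 11.4 that all analysis of safety is ruled out. The documents do not support that: what is excluded is statistical analysis.

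A reader might also infer that the decision to offer VR rests on benefit scores alone, so that a headset that made patients ill would be reported as a success. That too goes further than the text. The synopsis and section 1.2 state an aim, not a decision rule. Q19 to Q21 let intervention patients report increased distress or pain, Q22 and Q23 ask about satisfaction and willingness to use the intervention again, and section 11.2 says questionnaire responses will be summarised. The distress scale covers physical unpleasantness, so headset sickness could raise Q16. These are tolerability data, although they are not symptom counts and mostly have no control counterpart.

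Three further objections stand and limit the remedy:
- A formal test would have little power, so leaving it out is reasonable.
- Section 8.3 records adverse events, not refusals or early removal of the headset, so that item needs new recording. Control patients have no study intervention to stop, so a risk difference for it would be meaningless.
- Symptoms are not prompted by the survey and patients know their arm, so a by-arm count could be biased in either direction. The table must be labelled descriptive.

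None of this supplies the missing by-arm summary.

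**Conclusion.** The point holds as a minor gap in planned reporting. Adverse events must already be recorded in both arms, and no section tabulates them by arm, although the trial is meant to inform whether VR is worth offering. The conclusion rests on reading sections 8, 11 and 15 and Appendix B together, and does not depend on any assumed event rate.

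The size of the issue is one of interpretation. Zero VR events in 15 would still be compatible with a rate of up to 21.8%. An excess as large as 5 v 0 would reach the investigators and the DSMC as individual cases but would appear in no planned comparison. Nothing in the documents says that zero events would be called safe; the upper limit simply guards against that reading.

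A related inconsistency needs attention. Section 11.4 explains its approach by one-visit tracking, whereas section 8.2 follows events for 7 or 30 days after participation. A single visit would in any case not prevent tabulation by arm.

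**What to change.** Replace the last sentence of 11.4 with text such as:

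> Within each phase, the number and percentage of patients with any AE, and with each symptom listed in 1.3.1, will be tabulated by randomised arm, with exact 95% confidence intervals and the risk difference, without hypothesis testing. Zero counts will be reported with the upper confidence limit (21.8% for 0/15). The table will accompany any recommendation to offer an intervention.

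Three additions complete it:
- Report declining or stopping the intervention early for the intervention arms only, with one added record field, for example beside the comfort check in 6.3.
- State that the survey has no symptom item prompting AEs, so the table is descriptive.
- Reconcile the one-visit rationale in 11.4 with the follow-up window in 8.2.

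The cost is one table per phase and one record field, with no extra patients. The AE counts come from records that 8.3 already requires. The drawback is wide intervals, which will make the safety statement look less favourable than a bare count.

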14.1 Ethical Standard

The investigator will ensure that this study is conducted in full conformity with the principles set forth in The Belmont Report: Ethical Principles and Guidelines for the Protection of Human Subjects of Research, as drafted by the US National Commission for the Protection of Human Subjects of Biomedical and Behavioral Research (April 18, 1979) and codified in 45 CFR Part 46 and/or the ICH E6.

14.2 Institutional Review Board

The protocol, informed consent form(s), recruitment materials, and all participant materials will be submitted to the IRB for review and approval. Approval of both the protocol and the consent form must be obtained before any participant is enrolled. Any amendment to the protocol will require review and approval by the IRB before the changes are implemented in the study.

14.3 Informed Consent Process

Informed consent is a process that is initiated prior to the individual agreeing to participate in the study and continues throughout study participation. Extensive discussion of risks and possible benefits of study participation will be provided to participants and their families, if applicable. An e-consent form describing in detail the study procedures and risks will be given to the participant via the REDCap HIPAA-compliant platform. Consent forms will be IRB-approved, and the participant is required to read and review the e-document or have the e-document read to him, her, or them. Paper consent will be available at patient request. The investigator or designee will explain the research study to the participant and answer any questions that may arise. The participant will electronically sign the informed consent document prior to any study-related assessments or procedures.

Participants will be given the opportunity to discuss the study with their surrogates or think about it prior to agreeing to participate. They may withdraw consent at any time throughout the course of the study. A copy of the signed informed consent document will be emailed to participants for their records. If a participant does not have an email or does not wish to provide one, they will instead receive a paper copy of their consent form.

The rights and welfare of the participants will be protected by emphasizing to them that the quality of their clinical care will not be adversely affected if they decline to participate in this study. The consent process will be documented in the research record.

14.4 Exclusion of Women, Minorities, and Children (Special Populations)

Individuals of any gender, race, or ethnic background are eligible to participate. Individuals must be over 18 years of age as pediatric patients are not treated at the

outpatient medical oncology office, at [name], where BMBA procedures are performed.

14.5 Participant Confidentiality

Participant confidentiality is strictly held in trust by the investigators and study staff. This confidentiality is extended to cover all study information relating to participants. To ensure this protection, participants will be assigned a study ID number. This number will be linked to their study arm enrollment and associated questionnaires.

The study protocol, documentation, data, and all other information generated will be held in strict confidence.

15 Data Handling and Record Keeping

The investigators are responsible for ensuring the accuracy, completeness, legibility, and timeliness of the data reported. All source documents must be completed in a neat, legible manner to ensure accurate interpretation of data. The investigators will maintain source documentation, including survey records on the Qualtrics platform.

15.1 Data Management Responsibilities

Data collection and accurate documentation are the responsibility of the study staff under the supervision of the PI. All source documents must be reviewed by the study team and data entry staff, who will ensure that they are accurate and complete. Unanticipated problems and adverse events must be reviewed by the PI.

15.2 Data Capture Methods

Survey data will be captured through a Qualtrics survey and analyzed through the Qualtrics software. This is password/login protected and recognized as a Jefferson preferred, HIPAA-compliant survey system.

15.3 Types of Data

Survey questions, including patient demographics, will be collected pre- and post-procedure during Visit 1. Participant vital signs will be recorded as part of each patient's EMR. All data to be used in analyses will be deidentified and maintained on internal secure data servers.

A preliminary report will be generated following primary completion of Phase I. An additional report will be generated following primary completion of Phase II. The final report will look at data from both phases.

An interim report is due to the funding sponsor, the DAISY Foundation, after enrollment is complete. A final report is due after all analysis is complete.

15.4 Study Records Retention

Study records will be maintained for two years following study completion to allow for analysis and implementation into current processes.

15.5 Protocol Deviations

A protocol deviation is any noncompliance with the clinical study protocol, Good Clinical Practice, or Manual of Procedures requirements. The noncompliance may be on the part of the participant, the investigator, or study staff. As a result of deviations, corrective actions are to be developed by the study staff and implemented promptly.

All deviations from the protocol must be addressed in study participant source documents and promptly reported to the IRB and other regulatory bodies according to their requirements.

16 Study Finances

16.1 Funding Source

This study is financed through a grant from the DAISY Foundation.

16.2 Conflict of Interest

Any investigator who has a conflict of interest with this study (patent ownership, royalties, or financial gain greater than the minimum allowable by their institution, etc.) must have the conflict reviewed by a properly constituted Conflict of Interest Committee with a Committee-sanctioned conflict management plan that has been reviewed and approved by the study sponsor prior to participation in this study. All Jefferson University Investigators will follow the TJU Conflicts of Interest Policy for Employees (107.03).

Appendix A: Schedule of Events

Appendix B: Patient Survey

APPENDIX A: SCHEDULE OF EVENTS

Vital Signs – Heart rate, blood pressure, and respiratory rate.

| Procedures | | Screening (Day 1) | Study Visit 1 (Day 1) | Premature Discontinuation |
|------------------------------------|----------------------------|----------------------|--------------------------|---------------------------|
| Signed Consent Form | | X | | |
| Assessment of Eligibility Criteria | | X | | |
| Review of Medical History | | X | | |
| Study Intervention | | | X | |
| Physical Assessment | Pre-procedure Vital Signs | | X | |
| | Post-procedure Vital Signs | | X | |
| Assessment of Adverse Events | | | (X) | X |
| Survey | Distress Assessment | | X | (X) |
| | Pain Assessment | | X | (X) |
| | Satisfaction Questionnaire | | X | (X) |

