2.1 Objectives

2.1.1 Primary

To assess patient distress scores related to BMBA procedures.

The primary outcome will be reported on a scale of 0-10, based on the National Comprehensive Cancer Network (NCCN) Distress Thermometer. This scale is standardly used with oncology patients to determine their distress levels—distress refers to “an unpleasant experience of a mental, physical, social, or spiritual nature. It can affect the way you think, feel, or act. Distress may make it harder to cope with having cancer, its symptoms, or its treatment.”³⁰

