6.3 Treatment Period

Visit 1, Day 1

- Confirm patient is comfortable proceeding with assigned intervention during BMBA procedure.
- Standard of care BMBA procedure.
- Assess post-procedure vital signs: heart rate, blood pressure, respiratory rate.
- Administer post-procedure questionnaire, which includes:
 - Assessment of current distress level (0-10 scale).
 - 0-10 Numeric Pain Intensity scale.
 - Patient satisfaction questions.

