8.1.2 Adverse Events

An adverse event is any untoward or unfavorable medical occurrence in a human participant, including any abnormal sign (for example, abnormal physical exam or laboratory finding), symptom, or disease, temporally associated with the participant's participation in the research, whether or not considered related to the participant's participation in the research.

Potential adverse events include fainting or lightheadedness during or post-procedure, bruising resulting from needle insertion, prolonged bleeding at biopsy site, discomfort at the site during or post-procedure, infection, dizziness, nausea, disorientation, and vertigo.

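### Adverse events are to be assessed, but nothing in the visit steps or survey asks completers about the VR symptoms the plan names, so mild VR intolerance is likely to be under-recorded and recorded unevenly by arm

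*Combined protocol and SAP*

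**What the plan says.** Section 1.3.1 names the harm expected from Intervention 1: "Virtual reality may cause symptoms associated with motion sickness, including nausea, dizziness, disorientation, and vertigo". It adds mild eyestrain and headache. Section 8.1.2 carries four of these into its list of potential adverse events, which ends with "discomfort at the site during or post-procedure, infection, dizziness, nausea, disorientation, and vertigo". The same list opens with symptoms that any biopsy patient might have: "Potential adverse events include fainting or lightheadedness during or post-procedure".

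The Visit 1 steps in section 6.3 start with a check before the biopsy: "Confirm patient is comfortable proceeding with assigned intervention during BMBA procedure". The biopsy and post-procedure vital signs follow. The last step is "Administer post-procedure questionnaire, which includes" distress, pain and satisfaction. There is no adverse-event step.

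The schedule of events in Appendix A does have an adverse-event row, "Assessment of Adverse Events". It shows an (X) at Visit 1 and a plain X at premature discontinuation. The (X) has no legend.

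Section 8.2 sets a window from consent to 7 days for non-serious events and 30 days for serious ones. Sections 8.3.1 to 8.3.4 require relatedness, expectedness, CTCAE grade and treatment to be documented. Section 3.3 says there is no follow-up visit. Section 11.4 plans no statistical analysis of safety.

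**The concern.** The trial is meant to show whether VR is worth offering to BMBA patients generally (section 1.2). That judgement needs to know how well VR is tolerated as well as whether it lowers distress. The plan states in advance which symptoms VR can cause, yet the instruments applied to every patient do not ask about them.

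Without a standard question, recording depends on whether a patient mentions a symptom and whether a staff member pursues it. Staff randomize the patient, give the VR instructions and enter the arm into the survey (section 6.2, Appendix B), and no masking is described. They have more reason to ask about dizziness after a headset than after a control visit. Because lightheadedness is also listed as a possible event around the procedure, VR symptoms can be interpreted only against controls who were asked the same question.

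At stake is the tolerability record of patients who complete the visit with mild symptoms. A sparse record could be taken as good tolerability when it reflects only how the data were gathered.

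**Working it through.** **1. The plan's own design figure.** Section 11.3 states 82.8% power for 15 per arm, effect size 1.1, two-sided 5%, equal-variance t-test. With df = 15 + 15 − 2 = 28 and noncentrality 1.1 × √(15/2) = 3.01, the noncentral t gives 82.84%. The figure is reproduced. The present point does not depend on it and does not change it.

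**2. Where the named symptoms could be picked up.**
- *Section 6.2:* consent, eligibility, randomization, pre-procedure survey, vital signs, instructions. No symptom question.
- *Section 6.3:* a general comfort check before the biopsy, not stated to be recorded. Section 1.2 describes about 10 minutes of VR beforehand and about 20 during the procedure, so most exposure comes after this check. No later symptom question.
- *Survey Q1 to Q18:* demographics, history, distress, pain and satisfaction.
- *Q19 to Q23 (intervention arms only):* change in distress and pain, satisfaction, reuse. Nausea, dizziness, disorientation, vertigo, eyestrain and headache do not appear.
- *Q24 (not restricted by arm in the Appendix B notes):* free text with no symptom prompt.
- *Appendix A:* (X) at Visit 1, while the other rows scheduled for that visit carry a plain X. The only other use of (X) is for the survey rows at discontinuation, which section 6.4 leaves to staff judgement. A conditional reading is therefore plausible, but it is an inference.
- *Section 8:* defines the window and the attributes to record, not how events are elicited. With no follow-up visit, no contact method is given for the 7-day and 30-day windows.

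**3. Size under assumed rates.** The documents give neither a symptom rate nor a reporting rate, so both are assumptions shown over a range. With true rate r, reported fraction c and n = 15, expected recorded cases are 15 × r × c, and P(at least one recorded) = 1 − (1 − r × c)^15.

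| Assumed true rate | All elicited (c = 1) | Half reported (c = 0.5) | Quarter reported (c = 0.25) |
|---|---|---|---|
| 10% | 1.5 expected; 79% | 0.75; 54% | 0.375; 32% |
| 20% | 3.0 expected; 96% | 1.5; 79% | 0.75; 54% |
| 30% | 4.5 expected; 99.5% | 2.25; 91% | 1.125; 69% |

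For example, r = 0.20 and c = 0.25 gives 1 − 0.95^15 = 0.54.

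**4. Uneven reporting.** Suppose both Phase I arms had the same 20% rate, but half of cases were reported under VR and a quarter under Control. The expected counts would be 15 × 0.20 × 0.50 = 1.5 and 15 × 0.20 × 0.25 = 0.75. That is a twofold difference with no true difference behind it.

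**5. What full elicitation could deliver.** Observing 0 of 15 would still be compatible with a true rate up to 1 − 0.05^(1/15) = 18.1% (one-sided 95% bound), or 1 − 0.025^(1/15) = 21.8% (two-sided Clopper-Pearson).

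**The case against.** The strongest reply is that adverse-event collection is planned. Section 8 applies to all participants whether or not 6.3 repeats it. The schedule has an adverse-event row covering Visit 1. Discontinuation carries a plain X, and section 4.4.2 has those who stop because of an event asked for details, so the least tolerant patients are covered. History of vertigo is an exclusion. Section 15.5 mentions a Manual of Procedures, not among the documents, which might say how staff ask. Safety is not a study objective, and 15 per arm will not give a precise rate.

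Much of this stands, and it rules out three stronger readings.

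- A reader might infer that symptoms are recorded only when a patient volunteers them to staff. The documents do not support that. An assessment is scheduled, (X) is undefined rather than shown to mean optional, and Q24 gives patients a route that bypasses staff.
- A reader might infer that VR will be judged on favourable scores alone. Q19 to Q21 let patients say the intervention made distress or pain worse, Q22 allows dissatisfaction, and Q23 allows a refusal of reuse.
- A reader might infer that a null VR result could not be distinguished from benefit cancelled by VR sickness, since distress is defined as "an unpleasant experience of a mental, physical, social, or spiritual nature". But the primary score still measures the net effect, and Q19 to Q21 would show part of any worsening. Symptom data would help interpretation; their absence does not invalidate the comparison.

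The reply does not cover completers with mild symptoms. The survey is written out item by item and controlled by amendment. Followed as written, it yields no comparable symptom data from them in any arm. Q19 to Q23 are not shown to controls and do not say which symptom occurred.

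**Conclusion.** The point holds as a gap in how symptoms are elicited. Collection is planned, but the Visit 1 mark is undefined, section 6.3 has no matching step, and no survey item asks completers about the VR symptoms named in sections 1.3.1 and 8.1.2. Under-recording and uneven recording by arm are likely consequences; the documents do not prove that they will occur.

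The size depends wholly on assumed rates. Over true rates of 10% to 30%, quarter reporting lowers the chance of seeing even one VR case from between 79% and 99.5% to between 32% and 69%. The consequence is confined to what the trial can say about VR tolerability. The primary comparison and the stated power are untouched. This is a cheap improvement worth making, not a flaw that undermines the trial.

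**What to change.** 1. Add one closed item to the post-procedure survey, shown to all arms including Control: since entering the procedure room, any nausea, dizziness or lightheadedness, disorientation, spinning sensation, eyestrain, headache, or none, with each symptom graded none, mild, moderate or severe.
2. Place it after Q23 and before Q24, outside the display rule that hides Q19 to Q23 from controls. There it cannot prime Q16 to Q18 or Q19 to Q23.
3. Change the Visit 1 adverse-event mark in Appendix A to a plain X, and list the assessment as a step in section 6.3.
4. Tabulate the item descriptively by arm within each phase, without a test.

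The cost is under a minute per patient, one descriptive table, and a short amendment to Appendices A and B and section 6.3; the protocol requires an amendment for appendix changes. More Grade 1 and 2 events will be recorded, which section 8.4.1.2 already sends to continuing review. With 15 per arm the estimates will be imprecise, and the report should say so.
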